#### Table 1 Schedule of Assessments

Tests & Procedures / Visit Name	Pre- Screening Visit	Screening Visit	reening Visit Cy		Cycle 2+	End of Treatment Visit	30-day Safety Follow-up	Overall Survival Follow-up	
Day	NA	0	1	15	1	Within 7 days after last dose of derazantinib or decision to permanently stop dosing	30+ days after the last dose of derazantinib	At least every 3 months from date of last dose of derazantinib	
Window	NA	-28 to -1	0	± 3 days	± 3 days	NA	NA	±14 days	
Written informed consent	$X^1$	X 						•	
Medical history	X	X		1			20 	2	
QLQ-C30, QLQ-BIL21, EQ-5D, G-SET/HTI questionnaires (prior to seeing physician)			$\mathbf{X}^2$		$\mathbf{X}^2$	X 	X 		
Physical examination		X	Х	X	Х	X	X		
Complete opthalmological examination		x			X 	x	X 		
ECOG performance status	X	X	Х	X	Х	X	Х		
Vital signs 		X	X	X	Х	Х	X	0	
12-Lead ECG, in triplicate		X 	X5	X5	X5	X 			
Blood for clinical blood tests 		X	Х	X	X	X	X	3	
Blood for serum pregnancy test		X 	$X^7$		$X^7$	X 	X 		
Blood for tumor markers, biomarkers, and ctDNA			X 		X 	X 			
Blood for pharmacokinetics		3	X9	X 	X9		2	2	
Urine for Pharmacokinetics					X 				
Tumor's genomic status 	X								
Tumor measurement and staging		X 			X 	X 	÷	0	
Concomitant medications		X 	$X^{15}$	X	X	X	X		
Adverse events assessment			Х	X	Х	X	X	8	
Derazantinib capsule dispensing 			Х		Х				
Derazantinib capsule accountability					x	x			
Survival contact 				-	3.		2	X	

F	
STATISTICAL ANALYSIS PLAN FINAL V	ERSION
BASILEA PHARMACEUTICA: DZB-CS-301 PAGE	9 of 35

22 AUGUST 2022

Consent can be obtained greater than 28 days prior to first dose and does not have to be repeated unless an updated, approved consent form is available. A patient can consent for tissue analysis and the full study separately or at the same time.

 EQ-5D, EORTC QLQ-C30 and QLQ-BIL21 questionnaires should be administered on Day 1 of the first cycle, every 8 weeks (two cycles) for the first six cycles (C3D1, C5D1, C7D1), once every 12 weeks (three cycles) thereafter (C10D1, C13D1, etc.), at the End of Treatment visit and at the 30 day Safety Follow-up. G-SET/HTI questionnaire should be administered on Day 1 of Cycle 3 and Day 1 of Cycle 5. EQ-5D should be completed first, followed by EORTC QLQ-C30, QLQ-BIL21 and G-SET/HTI, when applicable.

 Complete opthalmological examination will be performed at C2D1, C3D1, C4D1, C5D1, at the End of Treatment visit, and at the 30-day Safety Follow-up visit, and if clinically indicated (see Section 6.3 from the protocol).

 Vital signs include weight, temperature, blood pressure, respiration rate, and pulse. At the Screening visit, height will also be measured (see Section 6.2 from the protocol).  12-lead ECG in triplicate is required at Screening., on Day 1 and Day 15 of Cycle 1 (pre-dose, and approximately 6–8 hours after the dosing), on Day 1 of Cycle 2 (predose), on Day 1 of Cycle 3 (pre-dose, and approximately 6–8 hours after the dosing), on Day 1 of Cycle 4 and all subsequent cycles (pre-dose), and at the End of Treatment visit (see Section 6.4 from the protocol).

 Clinical safety blood samples will be forwarded to a central laboratory designated by the Sponsor for testing (see Section 6.5 from the protocol).

 A serum pregnancy test, if applicable, is required at Screening within 72 hours prior to dosing, and at the End of Treatment visit. In addition, serum- or urine pregnancy testing will be performed monthly (on Day 1 of each treatment cycle) while the patient receives study treatment, at the 30-day Safety Follow-up visit, and until 120 days after the last administration of study drug. (see Section 8.8.2 from the protocol).

 Blood samples for tumor markers, biomarkers, and ctDNA are only collected on Day 1 of Cycle 1 at pre-dose and every 8 weeks (two cycles) for the first six cycles (C3D1, C5D1, C7D1), once every 12 weeks (three cycles) thereafter (C10D1, C13D1, etc.), and at the End of Treatment visit. Blood samples for biomarkers and ctDNA will be collected only from patients enrolled after completion of the interim analysis, and subject to the granting of appropriate regulatory and IRB/IEC approval (see Section 6.7 and Appendix 3 from the protocol).

 Blood for sparse PK sampling is collected on C1D1, C1D15 and C3D1 at pre-dose (-1 hour) and 6-8 hours post-dose. Blood for PK is collected on Day 1 of Cycles 2 and 4 at pre-dose (-1 hour) (see Section 6.6 and Appendix 3). Blood for rich PK sampling for the PK/biomarker subgroup is collected on C1D1 and C2D1 pre-dose (-1 hour), and 1 ( $\pm$  5 minutes), 2 ( $\pm$  5 minutes), 4 ( $\pm$  15 minutes), 6 ( $\pm$  15 minutes), 8 ( $\pm$  30 minutes), 10 ( $\pm$  30 minutes), 12 ( $\pm$  30 minutes), and 24 hours after the daily dose of derazantinib (within 1 hour prior to the next dose), on C1D15 and C3D1, pre-dose (-1 hour) and between 6 and 8 hours after the daily dose of derazantinib, and on C4D1 pre-dose (-1 hour); the 10 and 12 h time-points are optional (see Appendix 3 from the protocol).

 In the rich PK sampling subset for urinary excretion: Urine for PK is collected on Day 1 of Cycle 2, starting from daily dose administration and until 24 h after dosing (immediately prior to the next dose) (see Appendix 3 from the protocol).

 The patient must test positive for *FGFR2* fusion (Substudy 1) or *FGFR2* mutation or amplification (Substudy 2). Details of FISH and NGS testing for this purpose are provided in Section 6.8, and summarised in Table 1 and Table 2 from the protocol.

 Tumor imaging assessments must be within 28 days prior to the first dose (see Section 6.9 from the protocol).

 Tumor measurement (CT/MRI scan of the chest, abdomen, and pelvis) and staging will be done every 8 weeks (two cycles) for the first six cycles (C3D1, C5D1, C7D1) and once every 12 weeks (three cycles) thereafter (C10D1, C13D1, etc.). Post-dose BS / WBMRI will be performed only if clinically indicated. If a scan shows CR/PR, a confirmation scan must be performed 4-5 weeks after the last scan was performed (see Section 6.9 from the protocol).

 Tumor measurement and staging will be performed at the End of Treatment visit only if the previous scan was not done within four weeks (28 days) prior to the End of Treatment visit or if the previous scan did not show radiographic disease progression (see Section 6.9 from the protocol).

 All medications taken within 30 days prior to the first dose are to be recorded.

 To avoid unnecessary waste of derazantinib capsules, in cases where treatment was interrupted and/or dose was reduced, the patient can continue dosing from the previously dispensed bottle until the next drug dispensing visit where re-supply is needed to maintain the protocol dosing regimen.

	23 AUGUST 2022
STATISTICAL ANALYSIS PLAN	FINAL VERSION
BASILEA PHARMACEUTICA: DZB-CS-301	Page 10 of 35

 Survival contact can be in person, via phone, or, where applicable, by checking regional/national death registries. All patients and/or family will be contacted at 3 month intervals ( $\pm$  14 days) to record the patient status as Alive (date); Dead (date); Alive, but withdrew consent for further follow up; Lost to Follow Up. Survival updates may be made more often than every 3 months if the patient is seen at the investigational site for other reasons and for study level survival sweep(s) (see Section 5.6 from the protocol).

#### 1.2 OBJECTIVES

#### 1.2.1 Primary objective

#### Substudy 1

• To evaluate the anti-cancer activity of ORR by central radiology review as per Response Evaluation Criteria in Solid Tumors (RECIST) version 1.1 in patients with inoperable or advanced iCCA whose tumors harbor *FGFR2* fusions and who received at least one prior regimen of systemic therapy.

#### Substudy 2

• To evaluate the anti-tumor activity of derazantinib by progression-free survival (PFS) at 3 months (PFS3) based on survival status or central radiology review (RECIST version 1.1) in patients with inoperable or advanced iCCA whose tumors harbor *FGFR2* mutations or amplifications, and who received at least one prior regimen of systemic therapy.

#### 1.2.2 Secondary objectives

#### Substudy 1 and Substudy 2

- To evaluate PFS by central radiology review and overall survival (OS)
- To evaluate duration of response (DoR) by central radiology review
- To evaluate the safety profile (toxicities) of derazantinib in this patient population
- To evaluate changes, and assess the minimally important difference, in HRQoL and symptom response from baseline using the EORTC QLQ-C30, QLQ-BIL21, G-SET / HTI, and the EQ-5D VAS

#### Substudy 2

• To evaluate the anti-cancer activity by ORR by central radiology review as per RECIST version 1.1 in patients with inoperable or advanced iCCA whose tumors harbor *FGFR2* mutations or amplifications, and who received at least one prior regimen of systemic therapy

### 1.2.3 Exploratory objectives

The exploratory efficacy objectives of this study are:

- To evaluate disease control rate (DCR) by central radiology review
- To evaluate time to progression (TTP) by central radiology review
- To compare TTP on the first and/or the last prior line of systemic therapy (reported) versus TTP on derazantinib by central radiology review (TTP will be calculated from the first date of receiving study drug or prior line of systemic therapy until radiographic disease progression)
- To evaluate ORR, PFS, DCR and TTP by investigator radiology review
- To evaluate the non-confirmed central and local ORR and DCR
- To explore the concordance of local FISH or NGS genomic testing compared to central FISH testing results

The exploratory PK and pharmacodynamic objectives of this study are:

- To evaluate changes in pharmacodynamic biomarkers
- To evaluate ORR, PFS, OS, and DoR by pharmacodynamic biomarkers

• To evaluate PopPK

• To evaluate the urinary excretion of derazantinib, and possibly its metabolites, in a subset of patients The PK and pharmacodynamic objectives and planned analyses will be further detailed in a separate plan. PK and pharmacodynamic data available at time of database lock and final analysis will be only be listed.

23 AUGUST 2022

# 1.3 STUDY ENDPOINTS

# 1.3.1 Primary Endpoints

# **Substudy 1**

ORR was selected as the primary endpoint of this study. This endpoint is an acceptable surrogate endpoint of clinical benefit in this disease. ORR will be the proportion of patients with confirmed complete responses and partial responses by central radiology review as per RECIST version 1.1.

# Substudy 2

PFS 3 will be the proportion of patients who have progression-free survival at 3 months from the first date of receiving study drug as assessed by survival status and central radiology review as per RECIST version 1.1.

# 1.3.2 Secondary Efficacy Endpoints

# Substudy 1 and Substudy 2

- PFS will be calculated from the first date of receiving study drug until radiographic disease progression by central radiology review or death
- OS will be calculated from the first date of receiving study drug until death.
- DoR will be calculated from the first date of documented tumor response to disease progression by central radiology review.
- Changes in HRQOL and symptom response will be evaluated using the EORTC QLQ-C30, QLQ-BIL21, and EQ-5D VAS.

#### Substudy 2

• ORR will be the proportion of patients with confirmed complete responses and partial responses by central radiology review as per RECIST version 1.1.

# 1.3.3 Exploratory Efficacy Endpoints

# Substudy 1 and Substudy 2

- DCR by central radiology. DCR will be the proportion of patients with confirmed complete or partial responses or stable disease by central radiology review as per RECIST version 1.1.
- TTP will be calculated based on central radiology review from the first date of receiving study drug until radiographic disease progression
- TTP will be assessed for the first and/or the last prior line of systemic therapy (reported) and will be compared to TTP on derazantinib
- ORR, PFS, DCR and TTP by investigator radiology review
- Non-confirmed central and local ORR and DCR
- Concordance of local FISH or NGS genomic testing compared to central FISH testing results

# 1.3.4 Safety Endpoints

Toxicities will be evaluated using National Cancer Common Terminology Criteria for Adverse Event (NCI CTCAE) version 4.03 criteria.

# 1.4 SAMPLE SIZES AS PER PROTOCOL, INTERIM ANALYSIS AND DATA MONITORING COMMITTEE

## Data Monitoring Committee (DMC)

The DMC was established to ensure the safety of study patients and the validity of study results. The DMC composition and operation was as described in the DMC Charter. The DMC may recommend study termination or continuation based on periodic review of safety and/or efficacy data in this study.

#### **Substudy 1**

To prove the drug effect over placebo in ORR in this single-arm pivotal study, the hypothesis was specified as

$$H_0: ORR \le 0.10 \text{ and } H_a: ORR \ge 0.10.$$

The hypothesis test will be performed at a one-sided 2.5% significance level. A 10% response rate is chosen for the null hypothesis (H0), which is much higher than the observed placebo rate  $7\sim8\%$  in larger historical trials and publications (Lamarca 2014). The 23% response rate under the alternative hypothesis is estimated for power and sample size calculations.

Approximately 100 patients will be enrolled for this two-stage group sequential study with futility stopping.

An interim analysis for futility was planned to be performed when 40 patients who satisfy mITT criteria had at least one post baseline tumor evaluation. The study was to be terminated for futility if 4 or fewer responses were observed among 40 evaluable patients. If the treatment was ineffective, i.e., ORR=0.1, the probability of futility stopping was 63%. If the true response rate ORR=0.23, the probability of futility stopping was only 3%. The design provided approximately 90% power to reject the null hypothesis at one-sided significance level 0.025, or equivalently to have the lower bound of confidence interval of ORR > 10%. If 5 or more objective responses (OR) were observed and confirmed based on central radiology review prior to enrollment of 40 evaluable patients, the interim analysis was to be performed based on fewer than 40 patients.

The interim analysis was performed on 29 patients satisfying the mITT criteria. At the time of analysis 6 patients (21%) had a confirmed central PR, and futility was rejected per DMC recommendation.

#### Substudy 2

A Simon's two-stage design will be used in Substudy 2. The null hypothesis (H0) that the true 3-month rate of PFS 3 is  $p_0 \le 0.45$  will be tested against a one-sided alternative. In the first stage, approximately 15 mITT-evaluable patients will be accrued. If there are 7 or fewer patients with PFS 3 in these 15 patients, then Substudy 2 will be stopped. Otherwise, 28 additional mITT-evaluable patients will be accrued for a total of up to approximately 43. H0 will be rejected if a PFS 3 is observed in 25 or more of these 43 patients.

The type I error rate is 0.0481, and power is approximately 0.8 when the true PFS 3 rate for derazantinib is  $p_1 = 0.65$ .

If the required number of patients alive and without disease progression is reached before full enrollment to Stage 1, the decision to transition from Stage 1 to Stage 2 may be taken before Stage 1 is fully enrolled.

If the required number of patients alive and without disease progression is not reached at the time of full enrollment to Stage 1, further enrollment will be suspended to allow for all patients to be evaluated for PFS 3.

The analysis was performed on 14 patients satisfying the mITT criteria. The protocol defined threshold for stage transition and study continuation was achieved with 8 patients out of 14 patients in mITT population meeting the PFS3 criterion.

# 2 ANALYSIS POPULATIONS

Three analysis populations will be defined as follows:

# 2.1 SAFETY/INTENT-TO-TREAT POPULATION (ITT)

The Safety/ITT population for Substudy 1 will include all patients with locally or centrally confirmed *FGFR2* fusions/rearrangements who receive any amount of study drug.

The Safety/ITT population for Substudy 2 will include all patients with locally confirmed *FGFR2* mutations or amplifications who receive any amount of study drug.

All data from patients enrolled but not fulfilling the molecular entry criteria (and therefore not included in the Safety/ITT population) will only be listed.

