	A subset of up to 20 patients (PK subgroup) will be asked to participate in rich PK blood sampling and PK urine sampling to assess the renal excretion of derazantinib (and its metabolites) (see Section 6.6). Patients will be asked for a additional consent to participate in the blood/urinary PK assessments.
	Exploratory assessments of derazantinib (and possibly metabolites) will be investigated from the PK urine samples.
Statistical methods:	Substudy 1
	To prove the drug effect over placebo in ORR in this single-arm pivotal study, the hypothesis is specified as:
	H0: ORR = 0.10 and Ha: ORR=0.23.
	The hypothesis test will be performed at a one-sided 2.5% significance level. A 10% response rate is chosen for the null hypothesis, which is much higher than the observed ORR of $7\sim8\%$ in larger historical studies and publications (Lamarca 2014). The 23% response rate for the alternative hypothesis is estimated.
	Approximately 100 patients will be enrolled for this two-stage group sequential study with futility stopping. An interim analysis for futility will be done when 40 patients who satisfied modified intent-to-treat (mITT) criteria had at least one post-baseline tumor evaluation. The study will be terminated for futility if four or fewer responses are observed among 40 evaluable patients. *
	If 5 or more objective responses are observed and confirmed based on central radiology review prior to enrollment of 40 evaluable patients, the interim analysis may be performed based on fewer than 40 patients.
	T T T T T T T T T T T T T T T T T T T

\* The interim analysis was conducted on 8 January 2019; futility was rejected (informative p-value 0.0275).

Confidential - Proprietary information of Basilea Pharmaceutica International Ltd.

	
 
If the treatment is ineffective, i.e., ORR=0.1, the probability of futility stopping is 63%. If the true response rate ORR=0.23, the probability of futility stopping is only 3%. The design will provide approximately 90% power to reject the null hypothesis at one-sided significance level 0.025 or equivalently to have the lower bound of confidence interval of ORR ≥ 10%.
 
All patients who receive at least one dose of derazantinib capsules will be considered evaluable for safety analyses.
 

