# **10.1** Study populations

Four analysis populations will be defined as follows:

- Safety/ITT Population: All patients who receive any amount of study drug.
- Modified intent-to-treat (mITT) Population: All patients who receive any amount of study drug and have at least one post-baseline disease assessment.

- Per Protocol Population: All patients in the mITT Population who have no major protocol violations during the study, receive at least one cycle (28 doses) of ARQ 087, have at least one post-baseline efficacy measurement, and test positive for *FGFR2* fusion by the central laboratory.
- PK population: All patients who receive at least 1 dose of study drug and have at least one PK sample.
  - Rich PK population (with PK parameter determination): All patients enrolled in the subset who receive at least 1 dose of study drug and have at least one PK sample.
  - Urine excretion population: All patients who provide a full 24 h interval urine collection on Day 1 of Cycle 2.

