### 3.2 STATISTICAL METHODS

### 3.2.1 Disposition of Patients and Analysis Populations

Patient disposition will be presented by substudy and overall. Tabulation will include the following:

- Number (%) of patients treated
- Number (%) of patients who discontinued treatment and primary reason for discontinuation of treatment
- Treatment phase duration (months)
  - Where the treatment phase duration will be calculated as the time from C1D1 to EOT visit. If EOT visit was not performed, then the last study visit prior to EOT will be analyzed.
- Number (%) of patients who performed the 30-day Safety Follow-up visit
- Number (%) of patients who entered Survival Follow-up, their last outcome at time of analysis (alive, continuing in follow-up, dead, lost to follow-up, alive, withdrawal of consent from study follow-up)
- Study duration (months)
  - Where the study duration will be calculated as the time from C1D1 to last survival follow-up date, or death. If last survival follow-up date, or death is missing, then the last date of contact will be analyzed.

The table will be based on the Safety/ITT Population.

The number and percentage of patients in each analysis populations (Safety/ITT, mITT, PP), including reasons for exclusion from each analysis population will be presented for all patients enrolled i.e. patients signed with informed consent.

The number of patients by country and site will be presented by the Safety/ITT population.

The following by-patient listings will be presented by substudy,

- Patient eligibility with inclusion and exclusion criteria details
- Patient enrollment
- Patient disposition
- Analysis populations
- IPDs

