# 3.2.6 Study Drug Exposure and Compliance

Study drug exposure and compliance will be presented using the Safety/ITT population.

Exposure to study drug will be presented cumulatively.

The number of cycles of study drug received is defined as the total number of cycles where the patient has received at least 1 dose of study drug in each cycle, and excluding any cycle(s) where the patient has not been dosed. The study drug exposure is recorded for each cycle where the number of capsules dispensed and number of capsules returned will be entered; where the number of capsules returned is equal to the number of capsules dispensed, then this indicates that the patients were not dosed at this specific cycle.

Duration of study drug is defined as: (date of last dose – date of first dose) + 1. If the date of last dose is missing then this will be imputed as the date of the last study drug dispensed.

Dose intensity (%) is defined as the percentage of the study drug a patient has taken compared to the amount of study drug the patient was meant to take. This will be calculated as:

Total cumulative dose received (mg) / total cumulative dose planned (mg) \*100

Total cumulative dose received (mg) is defined as the sum of all dose (mg) as recorded from the study drug administration eCRF page using each entry (date of last dose –date of first dose) + 1 \* dose in mg. If the date of last dose is missing then this will be imputed with the date of the last study drug dispensed.

Similarly, the total cumulative dose planned (mg) is defined as the sum of all planned dose (mg) as recorded from the study drug administration eCRF page using each entry (date of last dose –date of first dose) + 1 \* 300 mg. If the date of last dose is missing then this will be imputed with the date of the last study drug dispensed.

Treatment compliance is defined as the percent of actual amount of drug taken relative to the planned amount. It is calculated according to the following formula for the entire study:

% compliance = (# of capsules dispensed - # of capsules returned)/{(# of days in the dosing interval)\*(# capsules per daily dose)}\*100

where the # of days in the dosing interval excludes any days that the patient was instructed to hold dosing due to an AE.

Treatment compliance will also be summarized categorically, considering cut-offs of 80% and 120% for compliance.

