#### 3.2.8 Analyses of Safety Data

Safety analyses will be performed for the Safety/ITT population.

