# 4 CHANGES FROM PLANNED ANALYSIS

- The protocol indicates the primary analysis population is restricted to FISH performed by a central laboratory. However, this was not the case and therefore reference to central FISH has been removed
- Safety/ITT Population has been updated from "All patients who receive any amount of study drug" to 2 separate definitions for each substudy to take into consideration the substudy that each patient was enrolled in:
  - The Safety/ITT population for Substudy 1 will include all patients with locally or centrally confirmed *FGFR2* fusions/rearrangements who receive any amount of study drug.
  - The Safety/ITT population for Substudy 2 will include all patients with locally confirmed *FGFR2* mutations or amplifications who receive any amount of study drug.
- The mITT population definition was updated from "All patients who receive any amount of study drug and have at least one post-baseline disease assessment." to "All patients in the Safety/ITT population, and have at least one post-baseline disease assessment (at least one post-baseline imaging assessment in accordance with RECIST 1.1, or documented clinical progression [every effort should be made to objectively assess radiographic progression]). Patients who have primary reason for discontinuation as death will be included in the mITT population."
- The PP population was updated from "All patients in the mITT Population who have no major protocol violations during the study, receive at least one cycle (28 doses) of ARQ 087, have at least one post-baseline efficacy measurement, and test positive for FGFR2 gene fusion by the central laboratory" to "will include all patients in the mITT population who have no important protocol (IPD) deviations which are determined to potentially impact efficacy analyses during the study. Protocol deviations will be identified prior to final analysis." This was to reflect the Labcorp standard to use "important" rather than "major", and furthermore to allow flexibility in defining those IPDs that may affect the efficacy endpoints.
- DCR has been added as an exploratory efficacy endpoint, and is defined as the achievement of confirmed CR or PR or SD (or Non-CR/Non-PD for patients with non-measurable disease).

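### SAP 2.1 makes a qualifying FGFR2 result a condition of the only safety population, so a dosed patient without one would be in the listings but in no safety, exposure or disposition table

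*SAP*

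**What the plan says.** Protocol 10.1 sets no molecular condition: "Safety/ITT Population: All patients who receive any amount of study drug". The protocol synopsis says the same in the statistical methods for each substudy: "All patients who receive at least one dose of derazantinib capsules will be considered evaluable for safety analyses". Protocol 10.3 plans the adverse event summaries for all enrolled patients. Protocol 6.11 requires safety data to be collected from a patient who turns out to be ineligible but has had at least one dose.

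SAP 2.1 requires dosing plus a molecular result. In Substudy 1 the result is a fusion or rearrangement found by a local or the central test. In Substudy 2 it is a mutation or amplification found locally. The section ends: "All data from patients enrolled but not fulfilling the molecular entry criteria (and therefore not included in the Safety/ITT population) will only be listed".

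The SAP then uses this set throughout:

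- Disposition (3.2.1), including the count of patients treated: "The table will be based on the Safety/ITT Population".
- Exposure and compliance (3.2.6): "Study drug exposure and compliance will be presented using the Safety/ITT population".
- Safety (3.2.8): "Safety analyses will be performed for the Safety/ITT population".

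SAP Section 4 discloses the change and describes it as a move to "2 separate definitions for each substudy to take into consideration the substudy that each patient was enrolled in".

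**The concern.** A safety population should contain everyone exposed to the drug, whether or not they turn out to have been eligible. The protocol commits to this and expects ineligible but dosed patients to contribute safety data. The SAP instead applies to safety a restriction that makes sense only for efficacy.

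The reason given in Section 4, that each patient belongs to one substudy, explains having two definitions. It does not explain why a molecular result should decide whether an exposed patient's adverse events are tabulated.

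At stake is whether the incidence rates and denominators in the safety tables describe all patients who took derazantinib. Excluded patients' events would remain in listings, but listings give no rates.

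**Working it through.** The plan states no figure for this group, so there is none to reproduce. The check traces each table to its population and then sizes the possible effect.

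**1. Is there another all-treated set?** SAP Section 2 defines three populations. Safety/ITT carries the molecular condition (2.1), mITT is a subset of Safety/ITT (2.2) and PP is a subset of mITT (2.3). A dosed patient outside Safety/ITT is therefore outside all three.

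**2. Which tables use Safety/ITT?** Disposition, exposure and compliance, and all safety analyses do, as quoted above. Nothing in 3.2.8.1 to 3.2.8.6 names a different set.

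**3. Where would such a patient be counted?** In one place: the table of population membership in 3.2.1, "including reasons for exclusion from each analysis population will be presented for all patients enrolled i.e. patients signed with informed consent". It gives membership and reasons only, with no events or exposure. It also covers everyone who consented, so it need not separate dosed from undosed patients.

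**4. Who is affected in Substudy 1?** A patient who is positive locally and negative or untested centrally stays in, because either result is enough. Only a dosed patient with neither a local nor a central positive result drops out.

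**5. Who is affected in Substudy 2?** The text points two ways. Protocol Appendix 8 bars certain aberrations, such as a concurrent FGFR2 translocation, even when an eligible mutation or amplification is present. A dosed patient with both has a locally confirmed mutation, and so meets the definition sentence of SAP 2.1. The same patient fails the molecular entry criteria, and so is removed by its last sentence. Two programmers could build different denominators.

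**6. Size.** Let k be the number of dosed patients left out of N dosed. The share missing is k/N. If E of the N had a given event, the tabulated rate lies between (E − k)/(N − k), when all k had the event, and E/(N − k), when none did.

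Take N = 100 from the planned Substudy 1 enrolment. E = 20 and the values of k are assumptions. The rate in all dosed patients is 20.0%.

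| k | Share missing | Lower bound | Upper bound |
|---|---|---|---|
| 1 | 1% | 19/99 = 19.2% | 20/99 = 20.2% |
| 5 | 5% | 15/95 = 15.8% | 20/95 = 21.1% |
| 10 | 10% | 10/90 = 11.1% | 20/90 = 22.2% |

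For Substudy 2, take N = 43, the planned mITT-evaluable number, as a stand-in for the number dosed. One excluded patient is 1/43 = 2.3% and five are 5/43 = 11.6%. With an assumed 4 events (4/43 = 9.3%) and k = 1, the bounds are 3/42 = 7.1% and 4/42 = 9.5%.

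**The case against.** The strongest case is that the group is close to empty by design. Substudy 1 dosing requires a local or central positive result, and Substudy 2 requires a positive NGS result. The investigator and the medical monitor confirm eligibility before enrolment, and waivers are not allowed. The one foreseeable sizeable group, local positive without central confirmation, stays in. Nothing in the documents says that any dosed patient lacks a qualifying result. This stands: the size is unknown and may be zero, and k = 10 is a generous assumption. It does not rescue the rule. SAP 2.1 contains a sentence written for this category, and if the group is empty the correction changes no safety result.

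A second argument is that SAP 3.2.1 equates enrolled with consented, so the sentence on listing may be aimed at pre-screening failures who never took drug. That reading is possible for the sentence alone. But the two definition sentences before it already require a molecular result in addition to dosing, so the exclusion of dosed patients does not depend on it.

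Third, the patients remain visible in the listings and in the membership table, Section 4 prints the old and new definitions, and a single-arm study with no testing of adverse event rates has no comparison to distort. All of this is true. There is no concealment, but a listing or a membership count does not replace a correct denominator.

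**Conclusion.** The concern holds. SAP 2.1 departs from the protocol's all-dosed safety set, no other population fills the gap, and Section 4 gives no reason for the molecular condition. This rests on the text alone.

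The practical effect cannot be computed from the documents. It may be nil; under the assumed values it runs from 1% to 10% of exposed Substudy 1 patients. The rate bounds above are extremes: if excluded patients resemble the rest, rates barely move and only the denominators are wrong.

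Correcting the safety set alters no primary endpoint, alpha or decision rule. SAP 3.2.7 does use the same Safety/ITT set for the Substudy 1 response rate, so the molecular condition reaches that denominator too. The change asked for here concerns safety, exposure and disposition only. It should be made, but it does not threaten the trial's main conclusion.

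**What to change.** In SAP Section 2, separate the two populations:

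- **Safety:** all patients who received any amount of derazantinib, by substudy and overall. Use it for disposition (3.2.1), exposure and compliance (3.2.6) and safety (3.2.8).
- **ITT:** the molecularly defined treated set, kept for efficacy. State whether a Substudy 2 patient with an aberration barred by protocol Appendix 8 belongs to it.

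Limit the listing-only rule in 2.1 to efficacy data. In the membership table, report the number of treated patients outside ITT, with reasons, separately from patients who consented but were never dosed. Give the reason for the molecular condition in Section 4.

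The cost is SAP wording and one additional population flag. No new data are needed.
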